**Visit 2 at 1-2 weeks from initiation of the combination therapy (sooner as clinically indicated)**

- i. A subject will be assessed for:
  - a. Medical history
  - b. Physical examination, including height and weight
  - c. Blood and urine tests, as clinically indicated
  - d. Additional organ function, as clinically indicated
- ii. Patients will be followed at no longer than two-week intervals over the first six weeks on trial, more frequently as clinically indicated. Note: participants in the dose escalation portion of the protocol will be followed via weekly visits, more frequently as indicated.

**Visit 3 at 2-4 weeks from initiation of the combination therapy (sooner as clinically indicated)**

- i. A subject will be assessed for:
  - a. Medical history
  - b. Physical examination, including height and weight
  - c. Blood and urine tests, as clinically indicated
  - d. Additional organ function, as clinically indicated
- ii. Patients will be followed at no longer than two-week intervals over the first six weeks on trial, more frequently as clinically indicated. Note: participants in the dose escalation portion of the protocol will be followed via weekly visits, more frequently as indicated.

**Visit 4 at 4-6 weeks from initiation of the combination therapy (sooner as clinically indicated)**

- i. A subject will be assessed for:
  - a. Medical history
  - b. Physical examination, including height and weight
  - c. Blood and urine tests, as clinically indicated
  - d. Additional organ function, as clinically indicated
- ii. Patients will be followed at no longer than two-week intervals over the first six weeks on trial, more frequently as clinically indicated. Note: participants in the dose escalation portion of the protocol will be followed via weekly visits, more frequently as indicated.

2. Assessment

- a. **At the 6 week (+/- 3 days) follow up visit, the degree of cGvHD will be formally re-assessed, again using NIH assessment and scoring forms (Attachment 1)**
- b. **After the 6 week follow up visit, patients may be followed at 2-4 week intervals, if clinically appropriate**
- c. Subjects may undergo repeat Rituximab weekly x4 therapy at 8 weeks after the initial therapy, depending on their prior clinical response
- d. **Formal re-assessment of cGvHD response via NIH criteria (Attachment 1 forms) will again be undertaken at the 3 month (+/- 7 days) and 6 month (+/- 7 days) follow up visits, to determine updated cGvHD status**
- e. If the subject shows progression of cGvHD, alternative treatment options will be discussed, including the appropriateness for removal from the study
- f. If the subject shows improvement (at least a partial response, by NIH response criteria), he/she will be continued on Ibrutinib for maintenance
- g. After 6 months, subjects will be followed for survival only.

Subsequent visits between the 6 week post-initiation period and 6 month follow-up timeframe will be at 2-4 week intervals, more frequently if clinically indicated (as outlined above). Serum biomarkers will be drawn at the 6 week, 3 month and 6 month post-initiation visits.

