## Study Summary

Title	Combination Ibrutinib and Rituximab for Treatment of Chronic Graft-Versus-Host Disease Following Allogeneic Stem Cell Transplant
Short Title	Ibrutinib and Rituximab for Steroid-Refractory or Dependent Chronic GVHD
Protocol Number	D17120
Phase	Phase 1/2
Methodology	Open label, Within-Subject Dose-Escalation Study
Study Duration	2 years (patients will be followed after 6 months for survival only)
Study Center(s)	Single center
Objectives	To determine the safety and efficacy of Ibrutinib and Rituximab combination therapy for steroid-refractory or -dependent chronic GVHD following allogeneic stem cell transplant.
Number of Subjects	15
Diagnosis and Main Inclusion Criteria	Steroid refractory or dependent chronic graft-versus-host disease (diagnosis to be based on histologic sampling and/or via clinical criteria; see Attachments) > 18 years old Karnofsky Performance Status 60 or greater

Study Product, Dose, Route, Regimen	
Within-Subject Dose-Escalation Format:
 
 
-The first 5 subjects will receive treatment as follows: 
 
-Ibrutinib 140 mg po once daily
 
-Rituximab 375 mg/m^2 IV weekly x4
 
 
 
-Adverse events will be defined as per the NCI Common Terminology Criteria for Adverse Events (CTCAE) 
 
-if no adverse events <math>\geq</math> non-hematologic grade 3 or <math>\geq</math> hematologic grade 4 are noted after 1 week at 140 mg daily, the Ibrutinib dose schedule will be increased to 280 mg daily
 
-if no adverse events <math>\geq</math> non-hematologic grade 3 or <math>\geq</math> to hematologic grade 4 are noted after 1 week at 280 mg daily, the Ibrutinib dose schedule will be increased to 420 mg daily
 
- the potential exists for a 2nd weekly x4 Rituximab course 8 weeks after initial Rituximab therapy, if no response or an incomplete response is noted
 
 
 
 
Expansion cohort:
 
 
- following accrual of the 5 initial subjects, an additional 10 subjects will be accrued, with dosing to be informed by the results of the within-subject dose escalation cohort
 

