Duration of administration	
Ibrutinib: ongoing (indefinite), with re-assessment of patient tolerance and response at 6 weeks, 3 months and 6 months
 
Rituximab: weekly x4, with or without a repeat 8 weeks after the initial therapy, depending on the patient's initial clinical response

Reference therapy	
Patients may have received steroids or other alternative GVHD regimens (with no new therapy for at least two weeks prior to the start of this protocol), without benefit,
 
OR
 
Patients may have shown an initial steroid benefit, but demonstrate an inability to undergo steroid taper due to persistent GVHD upon attempted steroid dose reduction.

Statistical Methodology	
GVHD response rates at 6 weeks, 3 months and 6 months will be assessed using exact binomial methods combining the initial dose escalation and expansion cohorts.
 
Univariate and multivariate analyses will be used to identify independent correlates of both safety and efficacy.

-------------------------	--------------------------------------------------------------------------------------------------------------------------------------------------------------------------------------------------------------------------------------------------------------------------------------------------

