## 3 Study Design

### 3.1 General Design

This is a non-randomized, open label, within-subject study to assess safety and preliminary efficacy for combination ibrutinib and rituximab in an allogeneic stem cell transplant recipient population, using a within-subject dose-escalation format.

Duration: 6 months, depending on response to therapy and ongoing clinical status.

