#### **Duration of therapy:**

Ibrutinib -> 420 mg daily (or adjusted dose) will continue until progression of cGVHD or development of significant side effects.

Rituximab -> there is the potential for a 2nd weekly x4 Rituximab course 8 weeks after initial therapy, if no response or an incomplete response is noted.

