### **Adverse Event Reporting Period**

The study period during which adverse events must be reported is normally defined as the period from the initiation of any study procedures to the end of the study treatment follow-up. For this study, the study treatment follow-up is defined as 30 days following the last administration of study treatment.

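### Follow-up after month 6 is for survival only, but ibrutinib may continue and adverse events are due until 30 days after the last dose, so the sections conflict and scheduled safety collection lapses

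*Combined protocol and SAP*

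**What the plan says.** **Follow-up.** Section 6 (Visit 4, Assessment, item g) reads "After 6 months, subjects will be followed for survival only". The Study Duration row of the Study Summary gives 2 years and adds that "patients will be followed after 6 months for survival only". Section 3.1 has a different length: "Duration: 6 months, depending on response to therapy and ongoing clinical status". Section 6 schedules visits every 2 to 4 weeks between week 6 and month 6 and describes none after that.

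**Treatment.** The Duration of administration row of the Study Summary has "Ibrutinib: ongoing (indefinite), with re-assessment of patient tolerance and response at 6 weeks, 3 months and 6 months". Section 5.1.1 (Duration of therapy, repeated in Section 8.5) says ibrutinib "will continue until progression of cGVHD or development of significant side effects". Section 5.1 allows it beyond 3 to 6 months as maintenance. Section 6, item f, immediately before the survival-only instruction, says of a subject with at least a partial response that "he/she will be continued on Ibrutinib for maintenance".

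**Adverse events.** Section 8.1 (Adverse Event Reporting Period) runs reporting to the end of study treatment follow-up and specifies that "the study treatment follow-up is defined as 30 days following the last administration of study treatment". Section 8.2 requires all adverse events in the study period to be recorded, and has them elicited by specific questioning whenever the subject is in contact with the investigator.

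**Late events.** Section 8.1 (Post-study Adverse Event) has subjects told at the last scheduled visit to report later events they believe related. It also asks the investigator to notify the sponsor of deaths or adverse events that may reasonably be related after participation has ended. Section 8.2 requires possibly related serious events after the study period to be recorded and reported.

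**The concern.** A responder at month 6 stays on ibrutinib. Under Section 8.1 that subject's adverse-event period is then still open, but the Section 6 schedule, from which site staff will work, reduces follow-up to vital status. Section 8.2 relies on contacts with the subject to elicit events, and after month 6 no safety contact is scheduled.

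Safety and tolerability is the primary objective (Section 2), and Section 3.2 sets no time window for the safety endpoint. Nothing in the plan therefore limits the eventual safety statement to the months in which events were actively sought. A report describing tolerability of continuing treatment could mix systematic data up to month 6 with sporadic reports afterwards, and the reasons subjects later stopped the drug might not be on record.

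**Working it through.** The plan gives no figure to reproduce here, so the check is mainly a comparison of the text.

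**Step 1: can a subject be on ibrutinib after month 6?** Yes. The Study Summary, Sections 5.1 and 5.1.1, and Section 6 item f all allow it. The only stops named in Section 5.1.1 are progression and significant side effects. Neither is a calendar date.

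**Step 2: is the adverse-event period still open for that subject?** If the ibrutinib is study treatment, yes: the period ends 30 days after the last administration, which has not yet occurred. Section 8.2 then requires all adverse events to be recorded, with no restriction by grade or seriousness.

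**Step 3: what does the schedule collect for that subject?** Survival only. The last visit, the last formal response assessment and the last stated tolerance re-assessment all fall at month 6.

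**Step 4: is ibrutinib after month 6 study treatment?** The documents do not say.

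- If it is, Steps 2 and 3 conflict for as long as the subject stays on the drug, plus 30 days.
- If it is not, and study treatment ends at month 6, Section 8.1 still runs 30 days past the point at which Section 6 turns to survival only. The conflict shrinks to those 30 days but does not vanish.

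**Step 5: what do the late-event provisions recover?**

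| Type of event after month 6 | Route in the plan |
|---|---|
| Serious, possibly related | Section 8.2, unscheduled report |
| Death or adverse event that may reasonably be related | Section 8.1, Post-study Adverse Event, unscheduled report |
| Non-serious and not judged related | No scheduled collection |
| Laboratory abnormality | No scheduled test; reported only if found and judged related |
| Reason for stopping ibrutinib | No scheduled collection |

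The first two routes are worded for events after the study period, or after participation has ended. A subject on drug and in survival follow-up has arguably reached neither point, so even these routes do not clearly apply.

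**Step 6: how much time is affected?** Only bounds on assumptions can be given.

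- If 2 years is per-subject follow-up: 24 - 6 = 18 months, and 18/24 = 75% of follow-up, for a subject who stays on drug throughout.
- If 2 years is the whole study with even accrual over 18 months: the first subject has 18 months left after month 6 and the last has 0, a mean of (18 + 0)/2 = 9 months.
- If the 6 months in Section 3.1 is the full study duration per subject: 0 months on study after month 6.

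The documents do not choose among these, and they do not project how many subjects will still be on ibrutinib at month 6.

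**The case against.** The strongest reply is that the sections can be read together. Item g may govern visits and assessments only, leaving adverse-event reporting to Section 8. If survival is established by speaking to the subject, Section 8.2's questioning applies at that contact. Ibrutinib after month 6 may also be ordinary care: Section 3.1 gives 6 months, Sections 5.8 and 5.10.1 have it filled at the patient's preferred pharmacy, and Section 1.1 notes its approval for chronic GVHD after failure of systemic therapy. Finally, Section 3.2 bases the primary endpoint on dose-limiting toxicities and the escalation results, and each escalation step is judged after 1 week.

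Much of this narrows the point. The endpoint as worded does not clearly depend on data after month 6, and the status of later ibrutinib is open. But the documents do not say how survival is ascertained, so a contact with the subject cannot be assumed. The indefinite duration in the Study Summary and the wording of Section 5.1.1 point towards continuing study treatment. A plan that needs this much interpretation will not be applied uniformly.

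A reader might go further and infer that late toxicity is lost altogether. The documents do not support that: Section 8.1, read literally, still requires reporting during treatment, and the late-event provisions keep related events reportable. A reader might also infer that long-term tolerability is overstated, but the plan makes no claim about tolerability beyond 6 months.

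**Conclusion.** The plan is wrong as written. For a subject still on ibrutinib after month 6, survival-only follow-up cannot be relied on to deliver the adverse-event recording that Sections 8.1 and 8.2 require. The loss is of scheduled ascertainment: non-serious events, laboratory abnormalities, events not judged related, and reasons for stopping the drug.

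The amount of exposure affected cannot be derived from the documents. At most it is 18 of 24 months per continuing subject, assuming the 2 years is per-subject follow-up and the subject takes ibrutinib throughout. It is tempting to turn this into person-years: 5 to 10 continuing subjects x 1.5 years = 7.5 to 15. That range is a ceiling resting on an assumed number of subjects, an assumed meaning of the 2 years and no stopping in 18 months, so it should not be quoted as an estimate.

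The dose-escalation decisions and the response-rate test in Section 7.1 are unaffected. What is at stake is the scope of the safety conclusion.

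**What to change.** Reconcile the Study Summary (Study Duration and Duration of administration), Section 3.1, Section 5.1.1, Section 6 items f and g, and Section 8.1. Begin by stating whether ibrutinib taken after month 6 is study treatment.

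- **If it is:** start survival-only follow-up at month 6 or 30 days after the last ibrutinib dose, whichever is later. Until then, name the contacts at which adverse events are sought, record them as Section 8.2 requires, and record the reason for stopping. If the sponsor wants only serious or higher-grade events after month 6, amend Sections 8.1 and 8.2 to say so; otherwise the restriction creates a new conflict.
- **If it is not:** amend Section 8.1 to say when the adverse-event period ends for subjects who continue ibrutinib, make Section 6 cover whatever period remains after month 6, and limit the safety and tolerability conclusion to the first 6 months.

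In either case, say whether the 2 years is per-subject follow-up or total study length. Neither option changes dosing or clinical management.

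The cost is protocol wording and, under the first option, a short case report form page and extra data entry for subjects still on drug. No clinic visits after month 6 are described, so the contacts themselves would have to be specified.

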## 7 Statistical Plan

## 7.1 Statistical Methods

GVHD response rates based on the GVHD Global Severity Score and Clinical Assessment ( Attachment 1) at 6 weeks, 3 months and 6 months will be assessed using exact binomial methods combining the initial dose escalation and expansion cohorts. With the expansion cohort after the safety dose escalation phase, a total of 15 patients will be available for evaluation. An exact test for proportions with a null hypothesis of a 15% response rate, an alternative hypothesis of a 50% response rate, and a one-sided significance level of 0.10, would have a power of 85% using 15 subjects, including a Bonferroni correction for looking at the 6 week, 3 month and 6 month response rates. This test rejects the null hypothesis if 6 out of 15 subjects respond. If only the 10 subjects from the expansion cohort are used, the null is rejected if 4 out of 10 respond, and the power is reduced to 0.83. Calculations were done in the PASS 2008 package.

Two-sample t-tests for continuous data and Fisher's exact test for binary data will be used to compare responders and non-responders for the purpose of identifying independent *biomarker* correlates of treatment response. The power and precision of these comparisons will depend on the number of responders and non-responders compared.

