## 7.2 Subject Population(s) for Analysis

Any subject withdrawing from the study prematurely due to toxicity will be evaluable for toxicity and will not be replaced. Subjects withdrawing from the study for reasons other than toxicity (eg, due to relapse of malignancy) will be replaced. All subjects remaining on the study for at least 6 weeks will be evaluable for efficacy.

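### The 85% power in Section 7.1 needs 15 evaluable subjects, but Section 7.2 does not guarantee 15: one early toxicity withdrawal gives 0.79 and two give 0.71

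*Combined protocol and SAP*

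**What the plan says.** Section 7.1 pools the dose-escalation and expansion cohorts and says: "With the expansion cohort after the safety dose escalation phase, a total of 15 patients will be available for evaluation". The design sets a 15% null rate against a 50% target in an exact binomial test, one-sided at 0.10, with a Bonferroni correction for the looks at 6 weeks, 3 months and 6 months. The stated power is 85% with 15 subjects, and the decision rule is given as a count: "This test rejects the null hypothesis if 6 out of 15 subjects respond". The Study Summary plans 15 subjects and makes no allowance for loss.

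Section 7.2, repeated in 4.4.1, sets three rules that determine how many subjects enter the test:

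- Toxicity: "Any subject withdrawing from the study prematurely due to toxicity will be evaluable for toxicity and will not be replaced".
- Other reasons for leaving, such as relapse of the malignancy: the subject is replaced, and no time limit is given.
- Efficacy: "All subjects remaining on the study for at least 6 weeks will be evaluable for efficacy".

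Neither section says how a subject who leaves before week 6 because of toxicity counts in the response rate. A cut-off is given only for 15 subjects and for the 10 expansion subjects alone.

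**The concern.** The power statement treats 15 as certain, while the population rules let the number move. A toxicity withdrawal before week 6 does not meet the 6-week condition and is not replaced, so on the natural reading the efficacy set falls below 15. In the other direction, a subject who leaves at week 8 for relapse is already evaluable and is also replaced, so the set can rise above 15.

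Toxicity exits are foreseeable under this plan. Section 4.4.1 lists a grade 4 or higher event, and inability to tolerate the dose, among the possible reasons for ending participation.

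At stake are the power that readers will attach to the trial's only formal efficacy test, and the risk that the denominator and the cut-off are settled after the responses are known.

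**Working it through.** **Inputs.** From 7.1: null rate 0.15, alternative 0.50, one-sided 0.10, three time points, n = 15, cut-off 6, power 85%. From 7.2: the replacement and 6-week rules. No withdrawal rate is given anywhere.

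**Formulas.** With X ~ Binomial(n, p), the level is P(X ≥ r | n, 0.15) and the power is P(X ≥ r | n, 0.50). The level allowed per time point is 0.10/3 = 0.0333. The cut-off r is the smallest count whose level is at most 0.0333.

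**Step 1: reproduce the plan.** At n = 15, a cut-off of 5 has level 0.0617, which is too high. A cut-off of 6 has level 0.0168. Power = 1 − (1 + 15 + 105 + 455 + 1365 + 3003)/2^15 = 1 − 4944/32768 = 0.849. Both stated figures are right, and the Bonferroni correction is in them: at 0.10 uncorrected the cut-off would be 5 and the power 0.941.

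**Step 2: vary the number evaluable.**

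| n | Cut-off at 0.0333 | Level | Power |
|---|---|---|---|
| 12 | 5 | 0.0239 | 0.806 |
| 13 | 6 | 0.0075 | 0.709 |
| 14 | 6 | 0.0115 | 0.788 |
| 15 | 6 | 0.0168 | 0.849 |
| 16 | 6 | 0.0235 | 0.895 |
| 17 | 6 | 0.0319 | 0.928 |
| 18 | 7 | 0.0118 | 0.881 |

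At n = 13 a cut-off of 5 just fails (level 0.0342). The cut-off is 5 for n = 9 to 12. At n = 18, keeping 6 gives level 0.0419, above 0.0333. (The 4-of-10 rule in 7.1 has level 0.04997, so it does not carry the correction. That is a separate matter.)

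**Step 3: keep early leavers in the denominator instead.** With d early toxicity withdrawals counted as non-responders and 50% response among those who stay, the denominator stays 15, the cut-off stays 6, and power = P(X ≥ 6 | 15 − d, 0.50):

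- d = 1: 1 − 3473/16384 = 0.788
- d = 2: 1 − 2380/8192 = 0.709
- d = 3: 1 − 1586/4096 = 0.613

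For one or two leavers this equals Step 2, because the cut-off is 6 either way. The two treatments part at three leavers: dropping them lowers the cut-off to 5 and returns power to 0.806, while counting them gives 0.613.

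**Step 4: an illustrative range.** Assume that each subject independently has a chance q of withdrawing for toxicity before week 6. The values of q are assumptions with no anchor in the documents.

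| q | P(all 15 evaluable) = (1 − q)^15 | Average power, leavers dropped and cut-off re-derived | Power, leavers as non-responders: P(X ≥ 6 given 15, 0.5(1 − q)) |
|---|---|---|---|
| 0.05 | 0.46 | 0.81 | 0.80 |
| 0.10 | 0.21 | 0.78 | 0.74 |
| 0.20 | 0.04 | 0.73 | 0.60 |

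**The case against.** The strongest reply is that nothing is miscalculated. The 85% and the 6-of-15 rule are exact at the planned n, and the design reaches them if nobody leaves early for toxicity. That stands. What fails is the unqualified statement that 15 will be available.

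A second reply is that 7.1 commits to an exact test and gives 6 of 15 only as its result at the planned n. Running the same test at the observed n would find the right cut-off unaided. This largely stands for the cut-off but does nothing for the power. A reader might infer that a fixed count of 6 is wrong as soon as n moves either way. The table shows otherwise: it takes three net losses or three net additions.

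A third reply concerns how likely losses are. A reader might infer that n = 13 is built into the plan, because 5.1.1 and 8.5 stop the study only when more than 2 of the first 5 subjects have a qualifying event at 140 mg. The documents do not support that step. Those sections speak of discontinuing treatment, whereas 7.2 counts time on the study, and a subject off drug but still followed at week 6 is evaluable. Nor does 7.2 expressly exclude those who leave before week 6; that is inferred from the 6-week condition. Step 3 answers the inference: for one or two leavers the power loss is the same if they are kept as non-responders.

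The 85% would survive early leavers only if they stay in the denominator and the 50% target already allows for them. No section says so.

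Finally, replacing a late leaver who is already evaluable raises n and power. Its only statistical risk is the level, and only if 6 is kept at n = 18 or more.

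**Conclusion.** The point holds as a qualification of a stated figure. The power of 85% is conditional on no early toxicity withdrawal, and 7.1 presents it without that condition. One such withdrawal costs 0.061 (0.849 to 0.788) and two cost 0.140 (0.849 to 0.709). This rests on the plan's own rates and per-look level, on 50% response among those who stay, and on early leavers being either dropped or counted as non-responders. How often such losses occur cannot be judged from the documents.

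The cut-off of 6 is sound for n = 13 to 17. Only n of 12 or fewer, or 18 or more, requires a different count.

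The weight is moderate. A reader might take the 85% as the trial's main or only operating characteristic. It is neither: 7.1 also gives 0.83 for the 10 expansion subjects, and response is a secondary endpoint under 3.3, the primary one being safety. The missing 3- and 6-month denominators are an omission of detail on which this conclusion does not rest.

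**What to change.** In 7.1:

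- State the rule as rejection when the exact one-sided p is at most 0.0333 at a given time point, with 6 of 15 as the example at the planned n.
- Restate power as 0.85 with no early toxicity withdrawal, 0.79 with one and 0.71 with two.

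In 7.2 (and the matching text in 4.4.1):

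- Limit replacement to subjects who are not yet efficacy-evaluable.
- Keep early toxicity withdrawals in the efficacy denominator as non-responders. The denominator then stays 15 and the cut-off stays 6. Toxicity losses cannot lower the bar, as they would if three were dropped and the cut-off fell to 5.

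The cost is two paragraphs of wording and a less favourable power statement, including 0.61 if three subjects leave early for toxicity. No patients are added.

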## **5.6 Prior and Concomitant Therapy**

### **5.6.1 Restricted and Allowable Concomitant Medications**

1. History of treatment with a tyrosine kinase inhibitor (eg, imatinib) or other significant CYP4A inhibitor within 2 weeks of enrollment is NOT allowed.
2. History of standard-dose Rituximab therapy within 6 months of study enrollment is NOT allowed.
3. Pre-transplant use of Ibrutinib for indications other than cGVHD (eg, lymphoma therapy) IS permitted.
4. Concomitant use of corticosteroids for cGVHD after transplant, prior to and during this study, IS permitted and anticipated (with no dose change allowed for a period of at least 14 days prior to enrollment).
5. Concomitant use of other immunosuppressive therapies prior to and during this study IS also permitted (with no dose change allowed for a period of at least 14 days prior to enrollment).
6. Doses of concomitant steroids and other immunosuppressants may be tapered during the study, as clinically feasible.
7. Study subjects may receive prophylactic antimicrobials, based on post-transplant status.

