### **5.7 Treatment Discontinuation and Subsequent Therapy**

If there is progression of disease on evaluation at 6 weeks, 3 months or 6 months, the patient will be considered for other secondary therapies, depending on the severity of the cGVHD and his/her overall clinical status. Other commonly used secondary therapies include Tacrolimus/sirolimus, Mycophenolate mofetil, extracorporeal photophoresis (ECP), JAK1/2 inhibitors and other monoclonal antibodies. Pulsed steroid therapy may also need to be considered in an effort to control the degree of GVHD as a purely temporary measure (ie, “bridge” to secondary therapy).

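### Sections 7.1 and 7.2 would count as a responder a subject who progressed and then improved on other cGVHD therapy, so a rejection at 3 or 6 months could not be attributed to ibrutinib plus rituximab

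*Combined protocol and SAP*

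**What the plan says.** Section 7.1 plans an exact one-sided test at 0.10, Bonferroni-corrected for three visits, with a "null hypothesis of a 15% response rate, an alternative hypothesis of a 50% response rate". The decision rule is: "This test rejects the null hypothesis if 6 out of 15 subjects respond". A second rule, 4 of 10, applies if only the expansion cohort is used.

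The text on other cGVHD therapy is spread over several sections:

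- **Section 5.6.1** requires stable steroid and immunosuppressant doses only for the 14 days before enrolment. Steroids may continue during the study, and so may other agents: "Concomitant use of other immunosuppressive therapies prior to and during this study IS also permitted". On later changes it says "Doses of concomitant steroids and other immunosuppressants may be tapered during the study, as clinically feasible". It does not bar increases or additions.
- **Section 5.7** says that a subject who progresses at 6 weeks, 3 months or 6 months will be considered for other secondary therapies. It adds: "Pulsed steroid therapy may also need to be considered in an effort to control the degree of GVHD".
- **Section 6, Visit 4** says that on progression "alternative treatment options will be discussed, including the appropriateness for removal from the study". Section 4.4.1 lists progression among the possible reasons for ending participation. Neither makes removal mandatory.
- **Section 7.2** sets the efficacy population: "All subjects remaining on the study for at least 6 weeks will be evaluable for efficacy".
- **Attachment 1** asks at each assessment whether immunosuppressant or steroid doses have changed. Neither section 7 nor the response table in Attachment 2 uses the answer.

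**The concern.** In a single-arm trial, a fixed null stands in for a control group. Beating 15% says something about the combination only if the counted responses could have come from the combination.

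Followed literally, the plan allows this course. A subject progresses at the 6-week assessment and receives another systemic agent or pulsed steroids. The subject stays on study, is better than at baseline at 3 months, and is counted toward 6/15. Section 5.1.1 continues ibrutinib only until cGVHD progresses, so this subject may no longer be taking it when counted.

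Improvement on steroids is possible in part of this population. Of the steroid-dependent group, the Study Summary says: "Patients may have shown an initial steroid benefit, but demonstrate an inability to undergo steroid taper". Section 5.7 also names several non-steroid agents.

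At stake is the protocol's only efficacy analysis with a stated decision rule and power. Two of its three visits come after the first assessment at which progression can lead to new therapy. The 6-week visit is less exposed but not immune, because section 5.6.1 does not bar dose increases before it. Responder status also defines the groups in the biomarker comparisons of section 7.1.

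**Working it through.** **Inputs from section 7.1:** n = 15, cutoff 6, null 0.15, alternative 0.50, one-sided 0.10 over three visits. The per-visit level is 0.10/3 = 0.0333. X is the number of counted responders, binomial(15, p).

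**1. The plan's own figures reproduce.**
- Power: P(X ≥ 6 | p = 0.50) = 0.8491 (stated 85%).
- Error: P(X ≥ 6 | p = 0.15) = 0.0168, below 0.0333.
- A cutoff of 5 would give 0.0617, above 0.0333, so 6 is the right cutoff.
- Expansion cohort: P(Y ≥ 4) with Y binomial(10, 0.50) = 0.8281 (stated 0.83).

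**2. How far the counted rate may rise.**

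| Counted rate | P(X ≥ 6) |
|---|---|
| 15% | 0.0168 |
| 18% | 0.0387 |
| 20% | 0.0611 |
| 25% | 0.1484 |

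Solving P(X ≥ 6) = 0.0333 gives p = 0.174. Solving P(X ≥ 6) = 0.10 gives p = 0.226.

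**3. What lifts the counted rate.** Suppose the combination's own rate is 15%, a share f of the other 85% receives added therapy before the visit, and a share r of those is then rated a responder. Then

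counted rate = 0.15 + 0.85 × f × r.

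The 0.0333 level is passed when f × r exceeds (0.1741 − 0.15)/0.85 = 0.028. In 15 subjects that is 15 × 0.0241 = 0.36 of an extra responder on average.

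**4. Illustration.** The documents give neither f nor r for this setting, so both are assumptions. For r, the only guide is section 1.1, which puts response to first-line steroids at 30% to 50%. Take f = 0.2:
- r = 0.3: 0.15 + 0.85 × 0.06 = 0.201, P(X ≥ 6) = 0.062.
- r = 0.5: 0.15 + 0.85 × 0.10 = 0.235, P(X ≥ 6) = 0.117.

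The expected number of extra counted responders is 15 × 0.051 = 0.77 and 15 × 0.085 = 1.28. With f = 0.1 and r = 0.3 the counted rate is 0.1755 and the probability 0.035, barely above the limit.

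**5. The same point without f and r.** If exactly one non-responder is converted by other therapy, 5 genuine responders are enough to reject. At a genuine rate of 15% that has probability P(X ≥ 5) = 0.0617, against 0.0168 for the rule as designed.

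**The case against.** The strongest reply is that the expected course after progression is to leave the regimen. Ibrutinib runs only to progression (5.1.1), progression is a listed reason to end participation (4.4.1), and section 5.7 concerns therapy after discontinuation and treats pulsed steroids as a temporary bridge. This narrows the pathway but does not close it. Stopping the drug is not leaving the study, removal is left to discussion, and no text says how such a subject counts at later visits.

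It is also fair that efficacy is a secondary objective and the study is described as preliminary. That limits the weight of the point. It does not remove the need for a counting rule.

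Five stronger readings are tempting, and the documents do not support them:

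- **The 6/15 rule is invalid.** It is a correct exact test of the counted rate against 15%. If the counted rate is truly 20%, rejecting 15% is not a false statement about that rate. The difficulty is attribution.
- **The inflation is known to be large.** No frequency of added therapy, and no response rate after it, is given. Assuming that more than half respond would exceed the first-line steroid range in section 1.1, in subjects whose steroids had already failed or could not be tapered.
- **The null should be raised instead.** Nothing in the documents says to what value, and counting all responses would also move the 50% alternative.
- **The missing source for 15% is itself an error.** It is a missing detail.
- **The clinician item makes matters worse.** Attachment 1 rates change from the preceding evaluation, but sections 5.1.2 and 6 set a pre-treatment baseline. What section 7.1 means by its clinical assessment is a separate question of response definition.

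**Conclusion.** The point holds as a gap in how responses are counted. Sections 7.1 and 7.2, read with 5.6.1, 5.7 and Visit 4, would credit the combination with a response reached on another agent, in both the 6/15 and the 4/10 analysis.

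The arithmetic for 6/15 stands. The margin is small: the Bonferroni level is lost above a counted rate of 17.4%, which needs only about 3% of non-responders to be converted. The range of 0.06 to 0.12 is an illustration that rests on f = 0.2, r between 0.3 and 0.5, and a genuine rate of exactly 15%. The true figure could be smaller, and is zero if every subject who progresses leaves the study and no dose is raised for cGVHD.

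The change should be made before responses are analysed, since a counting rule chosen afterwards would be open to bias.

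**What to change.** State the following in sections 7.1 and 7.2, as an analysis rule only. No treatment rule changes.

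1. Response at each visit is measured against the pre-treatment baseline.
2. A subject counts as a non-responder at an assessment, and at all later ones, if before it either (a) new systemic cGVHD therapy was started, or (b) steroids or another immunosuppressant were raised above the enrolment dose to treat cGVHD. The subject stays in the denominator.
3. Protocol premedication and the second rituximab course do not trigger the rule.
4. The rule applies to both the 6/15 and the 4/10 analysis.
5. A sensitivity analysis counts all responses regardless of added therapy.

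The Attachment 1 dose-change question flags the subjects concerned. Direction, dose and date must come from the medication record.

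**Cost.** Sample size and cutoffs are unchanged, and the extra data abstraction is small. Some power is lost if subjects who would have responded have a dose raised for cGVHD. At a 50% rate, if one subject of the 15 can no longer count, power is P(binomial(14, 0.5) ≥ 6) = 0.788. With two it is P(binomial(13, 0.5) ≥ 6) = 0.709. Without such losses it is 0.849. The numbers one and two are assumptions.
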